**Principal Investigator is ultimately responsible for all aspects of the project including:**

A. It is the responsibility of the PI to ensure that each subject is adequately informed and freely consents to participate in the research. The PI will personally ensure that every reasonable

precaution is taken to reduce risks to the study participants, including subjects who are enrolled initially but prove to be screen failures or for whom data is incomplete, unusable, and/or otherwise eliminated during analysis.

B. It is the responsibility of the PI to delegate responsibility to the research staff in a manner that is commensurate with the staff's training and qualifications.

C. It is the responsibility of the PI to ensure that all procedures associated with the research are performed in accordance with the protocol, including the schedule of events as applicable, with the appropriate level of supervision, only by individuals who are licensed or otherwise qualified to perform them under the applicable laws, regulations, and policies.

D. The PI will ensure adherence to the study protocol and monitor the informed consent process.

E. The PI will ensure that there are appropriate facilities and resources to conduct the research.

F. It is the responsibility of the PI to be available to the research staff as needed and to regularly review research processes and address any deficiencies identified through quality improvement processes. The PI may also contact funding partners to schedule an external assessment of his or her research through an on-site visit and a regulatory audit of the protocol file. The PI is responsible for maintaining documentation of any quality improvement process for their specific studies.

G. It is the responsibility of the PI to ensure that adequate staff, resources, and professional practices and standards of care are maintained at external performance sites.

H. It is the responsibility of the PI to evaluate the intermediate and final results of the project and to take a leading role in the preparation of the final report.

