**Study Design**

The study is designed as a double-blinded, interventional, randomized clinical study involving patients with NASH. A major research question is whether ingestion of lycopene stabilized with Lycosome™ formulated phosphatidylcholine chaperone can reverse clinical and laboratory manifestations of NASH. Therefore, the primary endpoint of the project is the size of the liver and parameters reflecting lipid accumulation in the hepatic tissue at the end of the interventional period. Changes in the activity of liver-specific enzymes and parameters of lipid homeostasis represent the secondary question since normalization of serum levels of hepatic enzymes represents another important criterion of liver damage and its reversal in NASH. Biochemical parameters in serum specimens will be investigated before commencing the study, at the intermediate time points of 1 month and in the end of the study after 2 months treatment. To assess changed in the liver span Ultrasonography was used before and in the end of the trial.

Subjects will be assigned to take orally once a day either capsules containing 450 mg of regular phosphatidylcholine or 450 mg of the same phospholipid in Lycosome™ formulation with 7 mg of lycopene (Cambridge, UK).

The formulations will be dispensed to the subjects during follow-up visits each month. Monthly visits are planned to determine compliance and adherence to the protocol. A basic medical check-up will be performed and subjects will be asked questions to determine adherence to the protocol during each visit.

Packaging and labeling of the study products will be carried out according to the guidelines of NIH and US Department of Health and Human Services as recommended for biologics and investigational health food products. The formulations will be shipped to the study site in specially designed containers with primary and secondary components. The container closure system will prevent exposure of the investigational products to light, moisture, temperature extremes and air. This packaging system guarantees stability of the product for intended use. Protection from microbial contamination will be provided by maintaining container integrity after the packaging system is sealed. An adequate and validated procedure was used for investigational product manufacture and packaging.

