All individual packages will be labeled with a numerical code. None of the volunteers or trial personnel will be informed of study group assignment for the duration of the study. Unblinding of the results is planned to be performed by an independent statistician who will be hired and assigned to the work at the end of the study period.

Upon arrival at the clinical site the study products will be inspected by the Medical Officer and Clinical Monitor, then placed in a locked room at the clinic. Only the Medical Officer, PI and Clinical Monitor will have access to the products during the study period. Each subject will be given a one month supply of the study product at the "zero" time point of the study and then subsequently for each month of the study period following verification of compliance with the study protocol.

Total study duration is six months with a medical check-up for each volunteer at the "0" time point of the study as well as at 1st month and at the 2nd, the end of the interventional period.

During the medical check-ups each volunteer will be subjected to thorough clinical and laboratory investigation. Clinical investigation will include reading the vital signs, determination of body mass index, anthropometry, blood pressure measurement and computed tomography (at the initial and final time points of the study). Among laboratory tests will be determination of fasting serum glucose and lipids (total cholesterol, LDL, HDL and total triglyceride

[figure not shown]

levels), determination of ALT and AST levels, alkaline phosphatase, gamma glutamyl transpeptidase, lactate dehydrogenase, total bilirubin, CRP, LDL oxidation and IOD. Moreover, serum lycopene concentration and lycopene isomer profile will be measured at the initial and final points of the interventional period. All volunteers will also be subject to a standard hematological investigation.

Results collected for each volunteer will be stored as both paper files and digital files in Excel format and will be available for access by the Medical Officer, Medical Monitor and PI. To avoid any bias each subject will be given a random computer code containing three numerical characters and three letters. Decoding of the individual results will be carried out by an independent statistician hired for the purpose.

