Packages containing the study formulations will be coded and blinded for both the subjects and medical personnel conducting the study. Only the Principal Investigator will be informed of package contents and the subjects belonging to each study group.

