## **12. ADVERSE EVENT REPORTING**

Occurrence of adverse events in subjects consuming lycopene and phosphatidylcholine is very unlikely. If any do occur it is the responsibility of the Medical Officer and the PI to determine and analyze adverse event cause.

Among adverse reactions could be skin rash, dyspepsia and nausea.

Occurrence of any of these will be considered as a reason for volunteer withdrawal from study participation.

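### The protocol calls the trial double-blind with no trial personnel told the assignment, yet it tells the Principal Investigator every subject's group while that person keeps trial duties open to bias

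*Protocol*

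**What the plan says.** All three statements about blinding stand in Protocol Section 6, Study Design.

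- The label: "The study is designed as a double-blinded, interventional, randomized clinical study involving patients with NASH".
- The general rule: "None of the volunteers or trial personnel will be informed of study group assignment for the duration of the study". An independent statistician, engaged only when the study ends, is to do the unblinding.
- The closing paragraph: packages are "coded and blinded for both the subjects and medical personnel conducting the study", followed by "Only the Principal Investigator will be informed of package contents and the subjects belonging to each study group".

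Other sections give the PI working duties. In the list of PI responsibilities under Key Roles: "It is the responsibility of the PI to evaluate the intermediate and final results of the project". In Section 12, if adverse events occur, "it is the responsibility of the Medical Officer and the PI to determine and analyze adverse event cause". Section 8 makes the PI and the Medical Officer jointly responsible for storing and dispensing the products.

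On laboratory data, Study Design says that "serum lycopene concentration and lycopene isomer profile will be measured at the initial and final points of the interventional period", and that each volunteer's stored results "will be available for access by the Medical Officer, Medical Monitor and PI". It makes no exception for lycopene.

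**The concern.** A protocol should give one answer to the question of who knows the allocation. This one gives two, and the second names the person with the widest set of duties. Someone who knows the arm may weigh a borderline adverse event or an ambiguous result differently in the two groups without intending to.

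Replacement adds to the exposure. Sections 12.2 and 17.1 replace withdrawn subjects from a pre-screened pool, so a withdrawal changes who makes up the group and does more than leave a gap. The grounds include adverse reactions, abnormal laboratory findings and poor adherence. Liver enzymes are themselves outcomes in these patients, so what counts as an abnormal laboratory finding leaves room for discretion.

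At stake is whether the report may call the trial double-blind, and whether causality judgements and replacements can be defended as made without knowledge of the arm. Once the PI has seen the allocation, the blind cannot be restored.

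**Working it through.** The main point needs no arithmetic. It rests on setting the text side by side.

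**1. Can the two rules be read together?** The general rule covers all trial personnel for the whole study. The PI is trial personnel. The closing paragraph gives the PI both the package contents and the group of each subject. It mentions no emergency, no sealed code and no point in time, so it does not read as ordinary emergency code-holding. The rules conflict.

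**2. Is the PI kept away from the data and the judgements?** No.

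| Duty | Place in the protocol |
|---|---|
| Shares storing and dispensing of the products | Section 8 |
| Access to the products and to each volunteer's results | Section 6, Study Design |
| Told at once of any possible adverse reaction | Section 12.1 |
| Determines adverse-event cause, with the Medical Officer | Section 12 |
| Evaluates intermediate as well as final results | Key Roles |

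**3. The lycopene results.** Study Design names lycopene (7 mg) in one arm only, so a raised final value probably points to that arm. Three limits apply.
- Access is given to the Medical Officer, Medical Monitor and PI, not to clinic staff at large.
- Sampling is at the initial and final points only. The on-treatment value can affect end-of-study judgements, but not decisions taken before it exists. The release date is not stated.
- No serum distributions are given, and diet could blur the separation. The comparator is also described inconsistently: regular phosphatidylcholine in Study Design, a Lycosome formulation in Section 7.4.6, while the Lycosome Structure text puts lycopene in the outer layer. These descriptions must be reconciled before the strength of this route can be judged.

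**4. How large could the effect be?** The plan gives no figure. An illustrative ceiling for one mechanism assumes 20 per arm (Section 6, Sample Size), no true effect, normal outcomes, a two-sided t-test at 0.05, and replacement of the 2 active subjects with the worst final outcomes by random ones.
- The expected values of the two lowest of 20 standard normal values are −1.867 and −1.408. The shift in the active mean is (1.867 + 1.408) / 20 = 3.275 / 20 = 0.16 SD.
- In 400,000 simulated trials the false-positive rate favouring active rises from 2.5% to 8.5%. With the 40 per group of Section 13.2 it is 7.2%.
- If selection instead uses an earlier signal whose correlation with the final outcome is 0.3, 0.5 or 0.7 (assumed values), the rate with 20 per arm is 3.6%, 4.6% or 5.9%.

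**The case against.** The strongest defence concerns what follows from the contradiction, and most of it stands.

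- **Withdrawals.** A reader might infer that the unblinded PI decides who leaves. Sections 9 and 12.2 give that decision to the Medical Officer, who is meant to be blinded. Neither Section 12 nor Section 12.2 makes the PI's causality judgement a condition of withdrawal. Influence through the shared causality work is possible but not stated.
- **The 8.5% figure.** A reader might take it as the trial's real error rate. It supposes that someone can pick the subjects with the worst final outcome. Study Design and Section 7.4.2 schedule liver imaging only at baseline and end, although Section 11 also speaks of liver size at intermediate points. On the imaging schedule the final liver values are not available when subjects are withdrawn.
- **Allocation concealment.** A reader might infer that there is none. Section 7.4.1 uses a random number generator and treats the assigned group as final. It does not say who runs the list, and the protocol does not say when the PI learns the groups. Foreknowledge at first enrolment is not shown.
- **Liver measurement and choice of analysis.** Nothing says that the PI reads images, and Section 13.3 gives the analysis to an independent statistician.
- **Evaluating results.** The Key Roles list is general, and a PI evaluating final results after decoding is normal. The reference to intermediate results is harder to excuse.

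None of this removes the conflict between the two rules, or the overlap between knowing the allocation and judging adverse-event cause.

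**Conclusion.** The concern holds as an internal contradiction on blinding that must be corrected before enrolment. The protocol cannot claim that no trial personnel know the assignment while telling the PI every subject's group. Because the PI also shares dispensing, judges causality, sees individual results and evaluates intermediate results, that knowledge could bias causality judgements and replacement. This rests on the text alone and on no assumed figure.

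No numerical bias should be attached to it. The 8.5% rate and 0.16 SD shift are an upper bound for two replacements under perfect foresight of the final outcome, and should be labelled so or left out.

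The lycopene access is secondary. It could unblind end-of-study judgements by three named roles, assuming that serum values separate the arms and are released before lock. The documents establish neither.

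**What to change.** 1. In Section 6, Study Design, delete the disclosure to the PI and state one blinding rule, naming who is blinded and until when.
2. Name a holder of the randomisation list and package key until database lock who has no part in dispensing, outcome assessment, adverse-event causality or analysis. Two obvious candidates do not qualify. The independent statistician is engaged only at the end and, under Section 13.3, also analyses the data. Supplier staff review adverse events and their cause under Section 12.1.
3. Keep serum lycopene and isomer results out of the shared files until lock.
4. If the PI must remain unblinded, say so, remove the PI from causality judgement and result evaluation, and qualify the double-blind claim.

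The cost is small but not nil: an independent code-holder has to be found and named, and release of one assay is delayed. Sample size, visits and measurements are unaffected.

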### **Study Schema**

***Inclusion Criteria:***

1. Age 18 years and above with provision of consent.
2. Patients with definite or probable nonalcoholic steatohepatitis based on the results of computed tomography and laboratory tests which were obtained no more than 90 days prior to randomization with or without type 2 diabetes mellitus and insulin resistance.

***Exclusion Criteria:***

1. Current alcohol use for a period of 3 consecutive months.
2. Patients with heart failure.
3. Anamnestic indication of long-term alcohol use in the past.
4. Patients with acute kidney injury at the time of enrollment
5. Patients with CKD (Chronic Kidney Disease) or with serum creatinine > 1 mg/dL.
6. Patients with platelet count <100.000/mm^3
7. Patient with severe cases of type 2 diabetes mellitus with Hb A1c >11.0 %
8. Pregnancy.
9. Patients with hepatocellular carcinoma.
10. Patients who are not willing to participate in the study.
11. Patients with any form of decompensation at the time of enrollment in the study.
12. Patients with hepatitis C as defined by presence of HCV RNA or antibodies to HCV.
13. Hepatitis B as defined by presence of HBsAg.
14. Users of medications associated with NASH – tetracycline, amiodarone, tamoxifen, glucocorticoids, anabolic steroids.

**7. CLINICAL PROTOCOL****7.1 Introduction****Background**

Lycopene is a polycarbon polyunsaturated red pigment from certain fruits and vegetables (tomatoes, papaya, strawberries, red bell pepper and cherries) which belongs to the carotenoid family and has extremely powerful antioxidant properties in vivo and in vitro (1). There is a growing body of clinical evidence that introduction of lycopene into the human diet prevents multiple diseases such as prostate cancer, type 2 diabetes and atherosclerosis. Recent studies indicate that lycopene supplementation deeply affects liver functions (2). In particular, as shown under experimental conditions, lycopene can prevent development of steatohepatitis in rodents (3).

Steatohepatitis, otherwise known as fatty liver disease, is a common pathological condition of liver which is characterized by accumulation of lipids in the hepatic tissue (4). Steatohepatitis accompanies multiple internal diseases such as obesity, type 2 diabetes, insulin resistance and hyperlipidemia and may finally result in liver cirrhosis (5). Although the exact number of patients with steatohepatitis in the world is not precisely defined, this number may approach 250 million patients who suffer from obesity and type 2 diabetes (6). Methods for steatohepatitis treatment are not well defined or standardized as yet. Diet, exercise and antiglycemic drugs are believed to be helpful in management of steatohepatitis, however no specific medication has been proposed as yet (7).

However, there is recent evidence that vitamin E therapy may attenuate steatohepatitis development (8). This suggests that use of antioxidants, including lycopene, may represent a novel strategy in treatment of steatohepatitis (8).

## **7.2 Rationale**

Dietary factors are crucial for maintenance of liver health and prevention/treatment of liver disease (9). Epidemiological evidence suggests carotenoid intake, in particular lycopene intake, may normalize some hepatic functions and prevent liver disease (10). Nevertheless, the effect of lycopene on liver disease and steatohepatitis in particular remains poorly investigated. These effects are largely attributed to the antioxidant properties of carotenoids. Amongst these antioxidants lycopene represents the most powerful agent capable of neutralizing superoxide radicals, nitric oxide and hydroxyl radicals under in vitro and in vivo conditions (11). Carotenoids are known to decrease plasma

[figure not shown]
activities of liver specific enzymes including alanine aminotransferase, aspartate aminotransferase and gamma-glutamyl transpeptidase (12). Carotenoids have also been shown to stabilize bilirubin level and increase bile production (13). Each of these changes was described in experimental models of liver disease, therefore adequate clinical studies should be performed to confirm the hepatoprotective properties of carotenoids in clinical settings.

Phosphatidylcholine is an important molecules to help to scaffold lipid structure in cell membranes and in particular in hepatocytes. It has been used for treatment liver fatty disease and liver steatosis. However, the main limitation of its use is a poor compliance because to achieve therapeutic effect patients need to take 1 gram, or 2 grams, or 3 grams or even more. The main reason behind administration of such high doses is that phosphatidylcholine is very sensitive to acidic oxidation. Hence to pass the stomach acidic environment, it has been only available approach, until recently, to provide a significant excess of the phospholipid to allow its to be oxidised in order to provide a smaller part to reach the intestine.

Development of Lycosome technology, which uses acid-resistant carotenoids help to protect sensitive molecules from stomach degradation (14-16)

The lycosome phosphatidylcholine particles are composed of clusters of this lipid and surrounding lycopene aggregate structures (Figure 1).

Figure 1. Phosphatidylcholine lycopene Lycosomes  
*diameter from 0.5 to 5  $\mu$  - light microscopy.*

## **LYCOSOME STRUCTURE**

The lycosome is protected by an external layer containing lycopene. Moreover, the external layer contains an amphiphilic phospholipid (phosphatidylcholine) serving as a chaperone for lycopene and as an emulsifying as well as hydrophilizing agent. Lycosome particles contain only food-derived natural ingredients. Lycopene, used as a core-forming agent in lycosome particles, is derived from tomatoes, while phosphatidylcholine originates from egg yolk or soy beans. This resolves a biosafety issue. Moreover, besides an exceptional biosafety record and obvious impact on bioavailability of other nutraceuticals, lycopene inherently confers some measurable degree of cardiovascular and neoplastic protection. The cholesterol-lowering and anti-tumorigenic actions of lycopene arising from its antioxidant properties have been reported in multiple independent clinical trials.

Microencapsulation protocols based on lycosome technology open new horizons for targeted organ-specific delivery of nutraceutical and possibly pharmacological agents. Lycopene is known to be a powerful ligand for carotenoid receptors abundantly expressed in the liver, brain and certain other vital organs. Therefore, upon ingestion lycosome particles become bound and internalized in the tissues where carotenoid receptors are expressed to the highest degree creating thereby targeted traffic of nutraceuticals in the human body via the network of carotenoid receptors. Selective hepatic delivery of nutraceuticals and certain drugs is essential, since the liver is the central organ responsible for biotransformation and action of bioactive substances of foreign origin. Some nutraceuticals and drugs work exclusively through hepatic mechanisms and do not display any effect unless they are available in the liver. As we recently reported in the "Archives of Medical Sciences", lycosome formulation of simvastatin, a hepatoselective drug used for treatment of hypercholesterolemia and cardiovascular disease, has a superior cholesterol-lowering ability as compared to an unmodified formulation of the drug.

All of the reasons stated above create a rationale for the present clinical study, which is designed to investigate the effect of lycopene on progression and outcomes of nonalcoholic steatohepatitis.

### **7.3 Clinical Study Objectives**

### **7.3.1 Primary objective**

The primary objective of this clinical study is to verify the effect of a novel formulation of lycopene fused with phosphatidylcholine chaperone on liver size and function as well as progression and outcomes of nonalcoholic steatohepatitis (NASH).

